12. Treatment with any investigational therapy within 4 weeks prior to randomization.
13. Allergen immunotherapy within 6 months prior to randomization.
14. Serum creatinine, total bilirubin, ALT or AST > 2x the upper limit of normal (ULN) during screening.
15. History of malignancy within 5 years prior to randomization, with the exception of completely treated and non-metastatic basal cell carcinoma or squamous cell carcinoma of the skin.
16. History of a major psychiatric condition (including major depressive disorder, bipolar disorder, or schizophrenia), suicidal ideation, or suicide attempt.
17. Known active hepatitis infection.
18. Known history of human immunodeficiency virus (HIV) infection.

19. Documented history of parasitic infection, including skin parasites such as scabies, within 12 months prior to randomization.
20. Known active parasitic infection.
21. Regular long-distance running (e.g. 10Ks, marathons) or long-distance bicycling (e.g. 30 + miles) and/or strenuous physical activity (e.g. bodybuilding) within 2 weeks prior to randomization
22. Presence of any medical condition or disability that, in the investigator's opinion, could interfere with the assessment of safety or efficacy in this trial or compromise the safety of the subject, including clinically significant ECG abnormalities during screening.
23. History of hypersensitivity to serlopitant or any of its components.
24. Currently pregnant or breastfeeding, or male subject with a pregnant or breastfeeding partner
25. Females of childbearing potential who are unable or unwilling to practice highly effective contraception (pregnancy prevention); fertile male subjects who are unable or unwilling to use condoms with female partners of childbearing potential.

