6.2.4 Electrocardiogram

A standard 12-lead ECG will be performed as outlined in [Appendix A](#) and at unscheduled study visits when clinically indicated.

[figure not shown]

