The terms “severe” and “serious” are not synonymous. Severity refers to the intensity of an AE (e.g. mild, moderate, or severe pain); the event itself may be of minor medical significance (e.g. severe back pain). “Serious” is a regulatory definition, as defined above. Seriousness (not severity) serves as the basis for defining regulatory reporting obligations.

Severity and seriousness should be independently assessed when recording AEs and SAEs on the eCRF.

7.1.3 *Abnormal Physical Exam, Laboratory, Vital Sign, and Electrocardiogram Findings*

Abnormal physical exam findings that are clinically significant and are identified prior to the first dose of study drug should be recorded as medical history. New or worsening clinically significant abnormal physical exam findings identified after the first dose of study drug should be recorded as AEs.

Only abnormal laboratory, vital sign, and ECG findings that are considered clinically significant by the investigator (e.g. require active management or are associated with accompanying symptoms/signs) will be recorded as medical history or AEs on the eCRF. Abnormal laboratory, vital sign, and ECG findings that occur prior to the first dose of study drug should be recorded as medical history, and abnormal findings that occur after the first dose of study drug should be recorded as AEs.

If the clinically significant laboratory, vital sign, or ECG abnormality is a sign associated with a confirmed disease or condition (e.g. elevated creatinine in a subject diagnosed with chronic kidney disease), only the diagnosis (chronic kidney disease) needs to be recorded on the AE eCRF.

Separate instances of the same clinically significant laboratory, vital sign, or ECG abnormality across visits should not be recorded as separate AEs or SAEs unless their severity, seriousness, or etiology changes.

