8.10.3 Vital Signs

The observed data and change from baseline for each measurement day will be summarized with descriptive statistics.

8.10.4 *Electrocardiograms*

The overall ECG assessment (abnormal or normal) will be summarized along with a summary of how many subjects developed a post treatment abnormal result. The study relevance of the finding will be provided in a listing.

8.11 *Interim Analyses*

This study includes an iDMC that will review study results to identify potential safety concerns. The iDMC is not tasked with stopping the study early for efficacy or for futility determinations.

8.12 *Pharmacokinetics Data*

The PK data and analysis for serlopitant and metabolites will be reported in a PK report that will be a part of the clinical study report.

9 *ADMINISTRATIVE ASPECTS*

9.1 *Changes to the Protocol*

Protocol amendments must be made only with the prior written approval of the Sponsor. An investigator signature will be obtained for the initial protocol and any amendments. Substantial amendments will be provided to the appropriate regulatory authorities. No protocol changes affecting the following will be made without the written approval of the Sponsor and the responsible IRB or EC:

- Safety and/or eligibility of subjects
- Data integrity
- Study design or conduct
- Willingness of a subject to participate in the study

9.2 *Study Termination*

The Sponsor has the right to terminate this study at any time. Reasons may include, but are not limited to, evidence of a potential safety risk in this study or other serlopitant studies or poor enrollment, or the recommendation of the iDMC. A written statement fully documenting the reasons for study termination will be provided to the IRB or EC.

9.3 *Monitoring and Auditing Procedures*

The Sponsor will designate study monitors who will be responsible for monitoring the conduct of this study. A separate study Monitoring Plan will include details regarding the responsibilities of the study monitors, investigator responsibilities in providing access to records and addressing issues identified, the frequency and structure of monitoring visits, and adherence to subject confidentiality as outlined in the Informed Consent Form (ICF).

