2.3.9 Safety Parameters

Vital signs will include measurements of heart rate, sitting blood pressure, respiration rate, and temperature. A standard 12-lead ECG will be performed and centrally read. From this central read the following parameters will be available: RR, PR, QRS, QT, HR, QTcB, QTcF, and the “interpretation” (Normal or Abnormal). If the result is considered abnormal, the specific findings will also be provided. Physical examination abnormalities identified as preexisting before treatment will be recorded as medical history. Laboratory results identified as clinically significant and abnormal before treatment will be recorded as medical history or associated with an ongoing historical event. Clinically significant new or worsened abnormalities that appear after treatment will be recorded as AEs.

Vital signs, ECG parameters and relevant interpretations, and laboratory results will be listed.

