2.4 Study Day and Visit Windows

Summary tables will report data based upon the protocol scheduled time points (Weeks 2, 4, 6 and Follow-up). Assessment will be assigned to these time points based upon the study day they are performed on. The derivation of study day depends upon whether the event occurred prior to or after treatment. This results in the first day of treatment being on day 1 and the day prior to the first day of treatment being day -1. For events that occur prior to the first day of treatment the following definition is used,

$$\text{Study day} = \text{date of assessment} - \text{date of first treatment}.$$

For events that occur on or after the first day of treatment, a plus one is added,

$$\text{Study day} = \text{date of assessment} - \text{date of first treatment} + 1.$$

The analysis windows used to report non-daily endpoints as well as ItchyQoL, sPGA and PGIC are outlined in [Table 3](#). If more than one assessment is available within the range the assessment closest to the target day is reported for the analyses window. If two observations exist with the same distance to the target day, the first observation is used.

Table 3 Analysis Windows

Visit	Range	Target Day
Baseline	Day \leq 1	Day 1
Week 2	Day 2 to Day 21	Day 15
Week 4	Day 22 to Day 35	Day 29
Week 6	Day 36 to Day 57	Day 43
Week 10	> Day 57	Day 71

In addition to the analysis windows, data will be summarized at Follow-Up. The Follow-Up assessment will be the last assessment available that is at least seven days after the end of treatment. Should no post treatment assessments be available the subject will not have a follow-up assessment. While a Week 10 analysis window is defined, data tables will be limited to Baseline, Week 2, 4, 6 and Follow-up.

eDiary and actigraphy daily results (WI-NRS, AI-NRS, night-time scratching, sleep efficiency and mean activity during the sleep) will be summarized at Baseline, Week 2, 4, 6 and Follow-up. The seven days leading up to the time point (see [Table 4](#) range), will be used to create the summary measures unless the subject does not have at least seven results. In this case as many observations as are available within the complete data range will be used and additional data from the extended range (see [Table 4](#)) will be used until seven data points are achieved or the end of the extended range is reached. An example of this algorithm can be found in [Section 3.4.1](#).

Table 4 Daily Windows

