3.5.2 Clinical Laboratory Evaluations

Summary statistics for actual values and for changes from baseline will be tabulated for clinical laboratory results by analysis window. Shifts from baseline clinical laboratory values based upon the normal range will be tabulated. These tables will utilize the normal ranges provided for the individual sample.

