3.5.4 Electrocardiogram Results

The overall ECG assessment (abnormal or normal) will be summarized by treatment and analysis window. The QTcF values will be summarized by treatment and analysis window as both the QTcF value and change from baseline. A summary of the number of subjects with a value > 450, 480 and 500 and the numbers of subjects with change from baseline values > 30 and 60 by treatment and analysis window will be produced.

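### SAP 3.5.4 leaves out the count of subjects who developed a post-treatment abnormal ECG that Protocol 8.10.4 plans, and its by-window totals cannot supply it (minor safety-reporting gap)

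*SAP*

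**What the plan says.** Protocol 8.10.4 (Electrocardiograms) plans three things: the overall normal/abnormal assessment, "along with a summary of how many subjects developed a post treatment abnormal result", and a listing of the relevance of each finding.

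SAP 3.5.4 says "The overall ECG assessment (abnormal or normal) will be summarized by treatment and analysis window". It then adds QTcF values and changes from baseline, counts above 450, 480 and 500, and counts of changes above 30 and 60. It plans no count of subjects who became abnormal and no normal/abnormal shift table. No other SAP section supplies one or explains the omission.

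Four other provisions bear on the point:

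- SAP 2.3.9 makes the central read available as a binary interpretation and states: "Vital signs, ECG parameters and relevant interpretations, and laboratory results will be listed".
- SAP 3.5.2 does plan within-subject change for laboratory values: "Shifts from baseline clinical laboratory values based upon the normal range will be tabulated".
- Exclusion 22 (Protocol 4.3) refers to medical conditions "including clinically significant ECG abnormalities during screening", so abnormal reads that are not clinically significant can be present at baseline.
- Protocol 6.2.4 allows ECGs at scheduled times "and at unscheduled study visits when clinically indicated". For the visit windows, SAP 2.4 then says: "If more than one assessment is available within the range the assessment closest to the target day is reported for the analyses window".

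**The concern.** To say that a subject developed an abnormality, the post-baseline read has to be set against that subject's own baseline. A total of abnormal reads in a window does not do this. The protocol's own account of TCP-101 (section 1.3.2) shows the difference. One subject had a normal ECG at screening and Visit 4, then supraventricular extrasystoles and an ectopic atrial rhythm at Visit 6. Another had first-degree AV block at screening, Visit 4 and Visit 6. If both Visit 6 tracings are read as abnormal, a Visit 6 total counts them alike, although only the first subject developed the finding.

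At stake is a safety summary that the protocol promised and that would be absent from the planned tables. ECG change is a listed safety endpoint, and the schedule gives few chances to see it: ECGs are at screening, Week 2 and Follow-up only.

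**Working it through.** **1. Is the count really missing?** The two sections compare as follows.

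| Item | Protocol 8.10.4 | SAP 3.5.4 |
|---|---|---|
| Overall normal/abnormal summary | yes | yes, by arm and window |
| Number who developed a post-treatment abnormal result | yes | no |
| QTcF values, changes, threshold counts | no | yes |
| Listing | yes (relevance of finding) | in SAP 2.3.9 (parameters and interpretations) |

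**2. Can the by-window totals recover it?** Let n be the subjects in an arm with all three reads, and b, w and f the numbers abnormal at baseline, Week 2 and Follow-up. The number normal at baseline and abnormal at least once afterwards lies between

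max(0, w − b, f − b) and min(n − b, w + f).

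This is an arithmetic identity and holds whatever the drug does. The planned 150 per group (SAP 1.6) is used for n. The documents give no ECG abnormality rates, so b, w and f are assumed and varied, with no missing ECGs.

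| b / w / f | Lower bound | Upper bound |
|---|---|---|
| 15 / 15 / 15 | max(0, 0, 0) = 0 | min(135, 30) = 30 |
| 30 / 30 / 30 | 0 | min(120, 60) = 60 |
| 45 / 45 / 45 | 0 | min(105, 90) = 90 |
| 15 / 20 / 18 | max(0, 5, 3) = 5 | min(135, 38) = 38 |
| 0 / 15 / 15 | max(0, 15, 15) = 15 | min(150, 30) = 30 |

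A linear-programming search over all eight baseline/Week 2/Follow-up patterns gives the same limits. The last row shows that the count is not fixed even when nobody is abnormal at baseline, because the overlap between Week 2 and Follow-up is unknown.

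**3. How extreme are the upper limits?** They need every subject abnormal at baseline to read normal at both later visits, and no subject to be abnormal at both. Take the opposite extreme for 15 / 20 / 18, in which all 15 baseline abnormalities persist. New abnormals are then 20 − 15 = 5 at Week 2 and 18 − 15 = 3 at Follow-up, so between 5 and 5 + 3 = 8 subjects. The range is much narrower but still not a single number.

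**4. Unscheduled ECGs.** The Week 2 window is Day 2 to Day 21 with target Day 15 (SAP 2.4, Table 3). An abnormal unscheduled ECG on Day 8 is 7 days from target and a normal scheduled one on Day 15 is 0 days, so Week 2 is tabulated as normal. Day 8 is a telephone contact in the schedule, so this needs an unscheduled, clinically indicated visit. Follow-up has its own rule: the last assessment at least seven days after treatment ends. That too keeps one read per subject.

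**5. What the scheduled ECGs cover.** Follow-up is 28 ± 3 days after the Week 6 visit. With a half-life of 70 to 80 hours (Protocol 1.3.1), 25 × 24 / 80 = 7.5 and 31 × 24 / 70 = 10.6 half-lives. Week 2 is therefore the only scheduled ECG on study drug.

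**The case against.** The strongest reply is that nothing is lost. SAP 2.3.9 lists every interpretation, so the count can be made by hand from planned output. New clinically significant findings become adverse events and are tabulated by arm. SAP 3.5.4 also goes beyond the protocol on QTcF, which measures within-subject change directly. All of this stands, and it keeps the point small. It does not remove it. A listing is not the summary the protocol planned, and for laboratory values the SAP provides both. The adverse-event route is narrower: "Only abnormal laboratory, vital sign, and ECG findings that are considered clinically significant by the investigator" are recorded (Protocol 7.1.3), whereas 8.10.4 has no such restriction. QTcF thresholds are not designed to detect rhythm or conduction findings of the TCP-101 kind.

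It may also be said that a SAP can refine a protocol. It can, but here a planned safety summary disappears without a stated reason. If post treatment were read as after the end of dosing, the Follow-up total would still mix old and new abnormalities.

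A reader might infer three stronger things that the documents do not support:

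- **That the protocol promised a Week 2, on-drug, normal-to-abnormal count.** Section 8.10.4 names no visit, no on-drug restriction and no denominator. It promises one summary of subjects who developed an abnormal result.
- **That the ranges above are likely values.** They are logical limits under assumed totals, and the upper ends need complete reversal of baseline abnormalities.
- **That an ECG safety signal would go unseen.** The listing, the adverse-event tables and the QTcF tables all remain.

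**Conclusion.** The point holds as a minor inconsistency between protocol and SAP. SAP 3.5.4 omits, without explanation, the summary of subjects who developed a post-treatment abnormal ECG, and the totals by arm and window cannot supply it. What lacks a planned table is, in the main, new abnormal reads not judged clinically significant.

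The size cannot be put as a single figure, because the documents give no ECG abnormality rates. The illustrations assume 150 subjects per arm with complete ECGs; missing ECGs would add uncertainty. That the count cannot be recovered does not depend on the particular totals chosen, apart from special cases such as no abnormal ECG after baseline. Reading developed as normal at baseline and abnormal later is the natural meaning, though the protocol does not define it. Efficacy, alpha and power are not affected, and no data are lost.

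**What to change.** In SAP 3.5.4 add, by arm, a shift table of baseline read (normal, abnormal) by worst post-baseline read (normal, abnormal), using all post-baseline ECGs, scheduled or unscheduled. From it report the number and percentage of subjects with a normal baseline ECG and at least one abnormal post-baseline ECG, and state the denominator: subjects with a normal baseline ECG and at least one ECG afterwards. State also that the one-read-per-window rule of SAP 2.4 does not apply to this table. If the omission was deliberate, the SAP should instead say so and give the reason.

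A Week 2 shift would be a useful addition, because Week 2 is the only scheduled ECG on study drug, but it goes beyond what Protocol 8.10.4 specifies.

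The cost is a short SAP edit and one descriptive table from ECGs already read centrally, with no new visit, procedure or staff. The downside is one more descriptive comparison, in which a difference between arms may look notable by chance.

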8.10.2 Clinical Safety Laboratory Results

Clinical safety laboratory values will be measured by a central laboratory. Summary statistics for actual values and for changes from baseline will be tabulated for laboratory results by scheduled visit. Graphs of laboratory values over time will also be produced.

Subjects with clinical laboratory values outside of the normal reference range at any post-baseline assessment will be summarized. Shifts from baseline laboratory values will be tabulated.

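### QTcF outlier counts and lab summaries take one value per analysis window, so a for-cause ECG or lab near a scheduled visit can go uncounted

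*SAP*

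**What the plan says.** SAP 3.5.4 tabulates the overall ECG reading and QTcF by treatment and analysis window. It also gives the number of subjects above 450, 480 and 500, and the number with "change from baseline values > 30 and 60 by treatment and analysis window will be produced".

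SAP 3.5.2 treats labs in a similar way: "Summary statistics for actual values and for changes from baseline will be tabulated for clinical laboratory results by analysis window". The next sentence, "Shifts from baseline clinical laboratory values based upon the normal range will be tabulated", names neither a window nor a rule for choosing the value.

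SAP 2.4 applies the Table 3 windows to non-daily endpoints, which include ECGs and labs: "If more than one assessment is available within the range the assessment closest to the target day is reported for the analyses window". For ties, "If two observations exist with the same distance to the target day, the first observation is used". Follow-up takes the last assessment at least seven days after treatment ends. Week 10 is defined as a window but not tabulated.

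Protocol 6.2.4 foresees ECGs "at unscheduled study visits when clinically indicated", and Protocol 6.2.3 foresees labs on the same terms. Protocol 8.10.2 plans that "Subjects with clinical laboratory values outside of the normal reference range at any post-baseline assessment will be summarized". Protocol 8.10.4 plans a "summary of how many subjects developed a post treatment abnormal result". Neither summary appears in SAP 3.5.2 or 3.5.4.

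**The concern.** An outlier count should find the subject whose value crossed a threshold, whenever that happened. Choosing the value nearest a target day suits a table of means over time. For an outlier count it favours the routine measurement over the one taken because something looked wrong. Lab and ECG changes are named safety endpoints, and the categories that matter most, such as QTcF above 500, may hold very few subjects. Leaving out one such subject could change what the table appears to show.

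Week 2 is where this bites. For a subject who completes treatment, the only other scheduled post-baseline ECG is at Follow-up, 28 days (± 3) after the Week 6 visit. The Week 2 window also contains the days just after the loading dose.

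**Working it through.** **Inputs**
- Windows (SAP Table 3): Week 2 is Days 2–21, target 15. Week 4 is Days 22–35, target 29. Week 6 is Days 36–57, target 43.
- Scheduled visits (Protocol 6.5.5 and 6.5.7): Week 2 on Days 13–17, Week 6 on Days 40–46.
- Scheduled post-baseline ECGs (Protocol Appendix A, SAP Table 2): Week 2 and Follow-up only.
- Scheduled post-baseline labs: Week 2, Week 6, early treatment discontinuation (ETD) and Follow-up.
- Half-life (Protocol 1.3.1): 70–80 hours.

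**Rule.** A value on day d is displaced by a value on day s in the same window with target T if |s − T| < |d − T|, or if the distances are equal and s < d.

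**One case.** An unscheduled ECG on Day 19 is |19 − 15| = 4 days from target. A scheduled ECG on Day 15 is 0 days from target. The Day 15 value is reported, so a QTcF above 500 on Day 19 is not counted.

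**All on-treatment days, ECG.** Days 2–42 are 41 days. Removing the day of the Week 2 ECG leaves 40 on which one unscheduled ECG could fall.

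| Week 2 ECG on | Unscheduled ECG displaced on | Days lost of 40 |
|---|---|---|
| Day 13 | Days 2–12, 17–21 | 11 + 5 = 16 |
| Day 15 | Days 2–14, 16–21 | 13 + 6 = 19 |
| Day 17 | Days 2–12, 18–21 | 11 + 4 = 15 |

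A lone unscheduled ECG on Days 22–42 is kept, because no on-treatment ECG is scheduled in the Week 4 or Week 6 window.

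**Unscheduled labs, same days.** With visits on Days 15 and 43, the displaced days are 2–14, 16–21 and 36–42: 13 + 6 + 7 = 26 of 40. Other visit days give 19 to 26 of 39 or 40. The lowest case is Week 2 on Day 17 with Week 6 on Day 40 or 46: 11 + 4 + 4 = 19. An unscheduled lab on Days 22–35 is kept if it is the only one in that window.

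**ETD labs.** These are displaced only when a Week 2 sample already exists and the ETD visit falls late in that window. With the Week 2 sample on Day 13, 15 or 17, the lost ETD days are 17–21, 16–21 or 18–21, which is 5, 6 or 4 of 41. This assumes a follow-up visit on Day 43 for an ETD before Day 15 (a proxy for the protocol's last-dose rule) and 28 days after the ETD otherwise. On all other days the ETD sample is the value reported.

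**Follow-up ECG.** For a completer it comes 28 × 24 = 672 hours after Week 6. That is 672/80 = 8.4 to 672/70 = 9.6 half-lives, so it says little about QTcF on drug. Because the last value is taken, an abnormal result followed by a normal repeat appears at Follow-up as normal.

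**Direction and scale.** Anyone counted in some window would also be counted at any time after baseline, so the windowed count can equal the any-time count or fall below it, never exceed it. With an any-post-baseline worst-value count, 0 of 40 ECG days are lost. One subject in an arm of 150 is 1/150 = 0.67 percentage points.

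**The case against.** The best defence is that nothing disappears. SAP 2.3.9 lists all ECG and lab results and records clinically significant new or worsened abnormalities as adverse events. SAP 3.5.1 tabulates those by preferred term and by worst grade. This stands, and it means that such a value can still reach a table. But that route depends on investigator judgement, and a listing gives no count by arm. Fixed QTcF thresholds exist to supply a count free of that judgement.

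Loss is also conditional. A lone unscheduled ECG on Days 22–42 is tabulated, and so is one on Days 2–21 if the Week 2 ECG was missed. A post-treatment value up to Day 57 can still enter the Week 6 window. All of this is right and limits the point.

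A reader might infer more than the documents support:
- **That ETD values drop out of the QTcF counts.** No ECG is scheduled at ETD (Protocol 6.5.8 and Appendix A, SAP Table 2). For labs the loss is the narrow case worked above.
- **That the protocol promised worst-value QTcF counts.** Protocol 8.10.2 concerns labs out of range. Protocol 8.10.4 concerns normal or abnormal readings. Neither mentions QTcF thresholds or worst values. The threshold table is an SAP addition, and the worst-value row would be an improvement on it.
- **That the lab shift table is windowed.** The SAP does not say so; its basis is undefined. A normal-range shift also loses nothing when the reported value is already out of range in the same direction as the displaced one.

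**Conclusion.** The point holds in limited form. As written, SAP 2.4 and 3.5.4 leave a for-cause ECG on Days 2–21 out of the QTcF outlier counts whenever a Week 2 ECG lies nearer Day 15. The days at risk are 15 to 19 of 40, depending on the visit day. Unscheduled labs in the Week 2 and Week 6 windows are exposed in the same way in the windowed lab summaries, on 19 to 26 of 39 or 40 on-treatment days. Separately, and without any assumption, SAP 3.5.2 and 3.5.4 do not carry over the Protocol 8.10.2 and 8.10.4 summaries.

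These figures count possible days, not subjects. The documents give no rate of unscheduled ECGs or labs, so the number of subjects missed cannot be computed and may be zero. It is tempting to conclude that the active arms would look safer than they are. Only the within-arm direction follows from the rule; the effect on the comparison with placebo depends on rates that the documents do not give. The change is still worth making because it costs little and the rule can miss exactly the values that an outlier table is meant to show.

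**What to change.** - **SAP 3.5.4:** add an any-post-baseline row for each QTcF threshold and each change category. Base it on the subject's worst value over all scheduled, unscheduled and follow-up ECGs.
- **Protocol summaries:** restore the Protocol 8.10.4 count of subjects with a new abnormal ECG in SAP 3.5.4, and the Protocol 8.10.2 summary of out-of-range labs in SAP 3.5.2.
- **Lab shift table (SAP 3.5.2):** state that it uses the worst post-baseline value, including unscheduled and ETD samples. Where both directions matter, show the highest and the lowest value separately.
- **Windowed tables:** keep them for values over time.

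The cost is SAP wording and a few table rows. No new data are needed, since these results are already listed. The displayed outlier counts may look slightly less favourable.
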